**Since randomization did patient receive?**

**Corticosteroid:**  Yes  No If yes, total daily dose (prednisone equivalent):    mg  
 1 mg prednisone/methylprednisolone = 4 mg hydrocortisone; 1 mg dexamethasone = 25 mg hydrocortisone

**Inhaled vasodilator:**  Yes  No If "Yes": indicate agent(s) used and total hrs administered  
 Epoprostenol  Nitric Oxide Total hours administered:

**Vasopressor support since randomization**  Yes  No **If No proceed to question 25.**  
**(check all received and highest infusion rate for each):**

- Dobutamine        µg/kg/min OR  µg/min
- Dopamine        µg/kg/min OR  µg/min
- Norepinephrine        µg/kg/min OR  µg/min
- Epinephrine        µg/kg/min OR  µg/min
- Vasopressin     units/min
- Phenylephrine        µg/kg/min OR  µg/min
- Milrinone        µg/kg/min OR  µg/min

Total hours receiving vasopressor support:

**Laboratory data (if only one value, record in "Lowest" field and click "Single" box; if no data, click "None" box):**

**CBC values:**

WBC: Lowest:    Highest:    x1000/mm^3 Single  None

Hgb: Lowest:    Highest:    g/dL Single  None

Hct: Lowest:    Highest:    % Single  None

Platelets: Lowest:    x1000/mm^3 None

**Serum Levels:**

Potassium: Lowest:  .  Highest:  .  mEq/L Single  None

Bicarbonate: Lowest:   .  Highest:   .  mEq/dL Single  None

BUN: Lowest:   .  Highest:   .  mg/dL Single  None

Creatinine: Lowest:   .   Highest:     mg/dL Single  None

Glucose: Lowest:    Highest:    mg/dL Single  None

Magnesium: Lowest:  .  Highest:  .  mmol/L Single  None

Phosphate: Lowest:  .  Highest:  .  mg/dL Single  None

Albumin: Lowest:  .  Highest:  .  g/dL Single  None

Bilirubin: Lowest:   .  Highest:   .  mg/dL Single  None

Highest AST:     U/L None  Highest ALT:     U/L None

**Highest/Lowest finger stick glucose every 6 hrs randomization through 0600 the next day (if only single value, enter in "Lowest" field and check "Single value" box; if no data, check "None" box):**

Time Period	Lowest Glucose (mg/dL)	Highest Glucose (mg/dL)	Single value	None
Day of Randomization				
0001-600				
0601-1200				
1201-1800				
1801-2400				
0001-600				

SITE ID		PATIENT ID				LETTER CODE			

**Ventilator mode/parameters used since randomization:**  
(check all that apply, circle the current one)

**DRAEGER**

- PC-CMV     VC-CMV     SPN-CPAP/PS
- PC-AC     VC-AC     SPN-CPAP/VS
- PC-SIMV     VC-SIMV     SPN-PPS
- PC-BIPAP     VC-MMV     SPN-CPAP
- PC-APRV
- PC-HFO
- PC-MMV
- Other \_\_\_\_\_

**SERVO**

- VC-AC     BiVent
- PC-AC     PS
- PRVC     VS
- VC-SIMV     CPAP
- PC-SIMV     NIV
- PRVC-SIMV

**Extubated:**  Yes  No    If Yes, Date/Time of extubation: / /   TIME (0-2400)

**ARDSNet Ventilation Adherence Data (if still intubated and mechanically ventilated):**

Measured Tidal Volumes:    Lowest:  ml    Highest:  ml

Estimated hours patient ventilated with tidal volume > 7 ml/kg     .  hrs

Applied PEEP:    Lowest:  cm H2O    Highest:  cm H2O

Mean airway pressure:    Lowest:  cm H2O    Highest:  cm H2O

**Lung Physiology Parameters (recorded 0600-1000 day 1 post-randomization; If no data available, check "No values" box. If patient not intubated, check "Not intubated" box)**

Plateau Pressure:  cm H2O and associated PEEP:  cm H2O.

No values:     Not intubated:

**Arterial Blood Gas (if only one value, record in "Lowest" field and check "Single value" box. If no ABG data check "None" box)**

PaO2 /FiO2: Lowest:  mm Hg/  % Highest:  mm Hg/  % mm Hg

Single Value:     None:

**Fluid Management:**

Total Intake since randomization:  mL

Total Output since randomization (include dialysis/CRRT):  mL

**Plasma sample collected:**  Yes     No

Blood collected: / /  TIME (0-2400)    Processed: / /  TIME (0-2400)

Number 0.5 ml aliquots:  1     2     3     4     5     6     7     8     9     10

Date/Time placed in -80°C freezer: / /  TIME (0-2400)

Location in freezer: \_\_\_\_\_    Temperature reading on freezer: °C    -

SITE ID		PATIENT ID			LETTER CODE		

## DAILY DATA – Day 03

(to be obtained as close to 0800 as possible on day 2 after randomization)

Form Completed by \_\_\_\_\_

MONTH			D D		Y Y Y Y			TIME (0-2400)	

Vital status  Alive  Dead

If Dead Date/Time of death:

MONTH			D D		Y Y Y Y			TIME (0-2400)	

Cause of death (from discharge summary/discussion with ICU team), then skip to question 11.

- Respiratory failure  
  Cardiac (arrhythmia, ACS, cardiogenic shock)  
  Multi-organ failure  
 Refractory shock  
  Intraabdominal (perforation, compartment)  
  Withdrawal of care  
 Neurological devastation  
  Severe sepsis  
  Refractory acidosis  
  Hemorrhage

Still receiving NMB?  Yes  No

If No and discontinued in last 24 hrs, answer following questions:

Date/Time discontinued:

MONTH			D D		Y Y Y Y			TIME (0-2400)	

Reason for discontinuation:  Refractory bradycardia    Possible drug reaction

Decision of ICU provider    Decision of family    As per Study protocol

Date/Time: neuromuscular function (4 twitches/TOF) returned:

MONTH			D D		Y Y Y Y			TIME (0-2400)	

or  Did not return

Is patient in hypothermia group?  Yes  No   **If "No" skip to question 13**

Still being cooled?  Yes  No   **If "Yes" skip to question 14**

If No, when was cooling stopped?

MONTH			D D		Y Y Y Y			TIME (0-2400)	

Reason for discontinuation:  Refractory bradycardia with hypotension    Hemorrhage  
 Intractable ventricular arrhythmia    Decision of ICU provider    Decision of family

### Skip to question 14.

If in the Control arm, received therapeutic hypothermia in last 24 hrs?  Yes  No  N/A

Still intubated or receiving Assisted Breathing?  Yes  No  N/A

If No, when was patient extubated or UAB for ≤48 hours?

MONTH			D D		Y Y Y Y			TIME (0-2400)	

Was RRT started in last 24 hrs?  Yes  No  N/A

If RRT had been previously initiated has it stopped since randomization?  Yes  No  N/A

In the last 24 hrs did the patient have any of the following:

Bradycardia (with mean arterial pressure < 65 mm Hg or needing pressors)  Yes  No

Significant Bleeding (Required IR, Surgery or >3u pRBCs)  Yes  No

Diagnosis of new pneumonia  Yes  No

### Vital signs in last 24 hrs

Systolic BP: Lowest:    Highest:    mm Hg   Single

Diastolic BP: Lowest:    Highest:    mm Hg   Single

CVP: Lowest:   Highest:   cm H2O   CVP not available  Single

Mean arterial pressure: Lowest:    Highest:    mm Hg   Single

--	--	--	--	--	--	--	--

SITE ID    PATIENT ID    LETTER CODE

For each 2 hr block for the last 24 hrs record highest and lowest temperature and lowest SpO2 and the FiO2 and Mean Airway Pressure measured closest to the SpO2 reading. If only single temperature measurement for block, check "Single value" box. If no SpO2 measured for block, check the "None" box.

Time period	Temp (°C) If only one value record as "Low" and check box	Site of Temp measurement	Low SpO 2 (%) *	FiO 2 (%)	Mean airway pressure (cm H 2 O)
0801 to 1000	High:	 Esophageal  Urinary	None 		
	Low: 	 Peripheral  IV			
1001 to 1200	High:	 Esophageal  Urinary	None 		
	Low: 	 Peripheral  IV			
1201 to 1400	High:	 Esophageal  Urinary	None 		
	Low: 	 Peripheral  IV			
1401 to 1600	High:	 Esophageal  Urinary	None 		
	Low: 	 Peripheral  IV			
1601 to 1800	High:	 Esophageal  Urinary	None 		
	Low: 	 Peripheral  IV			
1801 to 2000	High:	 Esophageal  Urinary	None 		
	Low: 	 Peripheral  IV			
2001 to 2200	High:	 Esophageal  Urinary	None 		
	Low: 	 Peripheral  IV			
2201 to 2400	High:	 Esophageal  Urinary	None 		
	Low: 	 Peripheral  IV			
0001 to 0200	High:	 Esophageal  Urinary	None 		
	Low: 	 Peripheral  IV			
0201 to 0400	High:	 Esophageal  Urinary	None 		
	Low: 	 Peripheral  IV			
0401 to 0600	High:	 Esophageal  Urinary	None 		
	Low: 	 Peripheral  IV			
0601- to 0800	High:	 Esophageal  Urinary	None 		
	Low: 	 Peripheral  IV			

**In last 24 hours did patient receive?**

**Corticosteroid:** Yes No If yes, total daily dose (prednisone equivalent):    mg  
 1 mg prednisone/methylprednisolone = 4 mg hydrocortisone; 1 mg dexamethasone = 25 mg hydrocortisone

**Inhaled vasodilator:** Yes No If "Yes": indicate agent(s) used and total hrs administered  
Epoprostenol Nitric Oxide Total hours administered:

--	--	--	--	--	--	--	--	--	--	--	--

SITE ID PATIENT ID LETTER CODE

 **Vasopressor support in last 24 hrs**  Yes  No **If No proceed to question 23.**

**(check all received and highest infusion rate for each):**

- Dobutamine   .     $\mu\text{g}/\text{kg}/\text{min}$  OR   $\mu\text{g}/\text{min}$
- Dopamine   .     $\mu\text{g}/\text{kg}/\text{min}$  OR   $\mu\text{g}/\text{min}$
- Norepinephrine   .     $\mu\text{g}/\text{kg}/\text{min}$  OR   $\mu\text{g}/\text{min}$
- Epinephrine   .     $\mu\text{g}/\text{kg}/\text{min}$  OR   $\mu\text{g}/\text{min}$
- Vasopressin   .   units/min
- Phenylephrine   .     $\mu\text{g}/\text{kg}/\text{min}$  OR   $\mu\text{g}/\text{min}$
- Milrinone   .     $\mu\text{g}/\text{kg}/\text{min}$  OR   $\mu\text{g}/\text{min}$

Total hours receiving vasopressor support:

 Did the patient start proning  Yes  No or stop proning  Yes  No in the last 24 hours?

 **Laboratory data (if only one value, record in "Lowest" field and click "Single" box; if no data, click "None" box):**

**CBC values:**

- WBC: Lowest:    Highest:    x1000/mm^3 Single  None
- Hgb: Lowest:    Highest:   g/dL Single  None
- Hct: Lowest:    Highest:   % Single  None
- Platelets: Lowest:    x1000/mm^3 None

**Serum Levels:**

- Potassium: Lowest:  .  Highest:  .  mEq/L Single  None
- Bicarbonate: Lowest:   .  Highest:   .  mEq/dL Single  None
- BUN: Lowest:   .  Highest:   .  mg/dL Single  None
- Creatinine: Lowest:    Highest:    mg/dL Single  None
- Glucose: Lowest:    Highest:    mg/dL Single  None
- Magnesium: Lowest:  .  Highest:  .  mmol/L Single  None
- Phosphate: Lowest:  .  Highest:  .  mg/dL Single  None
- Albumin: Lowest:  .  Highest:  .  g/dL Single  None
- Bilirubin: Lowest:   .  Highest:   .  mg/dL Single  None
- Highest AST:     U/L None  Highest ALT:     U/L None

 **Highest/Lowest finger stick glucose every 6 hrs for last 24 hrs (if only single value, enter in**

Time Period	Lowest Glucose (mg/dL)	Date	Time	Highest Glucose	Date	Time	Single value	None
0601-1200								
1201-1800								
1801-2400								
0001-600								

**"Lowest" field and check "Single value" box; If no data, check "None" box:**

SITE ID		PATIENT ID				LETTER CODE			

If patient was extubated/UAB >24 hours ago, go to question 34

Ventilator mode/parameters used in last 24 hrs (check all that apply, circle the current one)

 DRAEGER	 SERVO
 PC-CMV  VC-CMV  SPN-CPAP/PS  PC-AC  VC-AC  SPN-CPAP/VS  PC-SIMV  VC-SIMV  SPN-PPS  PC-BIPAP  VC-MMV  SPN-CPAP  PC-APRV  PC-HFO  PC-MMV  Other _____	 VC-AC  BiVent  PC-AC  PS  PRVC  VS  VC-SIMV  CPAP  PC-SIMV  NIV  PRVC-SIMV

Extubated:  Yes  No    If Yes, Date/Time of extubation: / /    
MONTH D D Y Y Y Y TIME (0-2400)

**ARDSNet Ventilation Adherence Data (if still intubated and mechanically ventilated):**

Measured Tidal Volumes:    Lowest:  ml    Highest:  ml

Estimated hours patient ventilated with tidal volume > 7 ml/kg     .  hrs

Applied PEEP:    Lowest:  cm H2O    Highest:  cm H2O

Mean airway pressure:    Lowest:  cm H2O    Highest:  cm H2O

**Lung Physiology Parameters (recorded 0600 to 1000 day 2 post-randomization; If no data available, check "No values" box. If patient not intubated, check "Not intubated" box)**

Plateau Pressure: cm H2O and associated PEEP:  cm H2O.

No values:     Not intubated:

**Arterial Blood Gas (if only one value, record in "Lowest" field and check "Single value" box. If no ABG data check "None" box)**

PaO2 /FiO2:    Lowest:  mm Hg/ %    Highest:  mm Hg/ % mm Hg

Single Value:     None:

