### 1.2/ Study Aims and Objectives

We will conduct the CHILL-pilot single-center RCT of TH in patients with COVID-19 and ARDS with P/F < 250 to address the following specific aims:

1. **Aim 1: Analyze the safety and feasibility and the potential lung protective effect of treating patients with COVID-19 infection and ARDS with P/F < 200 with mild TH (core temperature 34°-35°C) + NMB for 48h compared with controls receiving standard temperature management.** We expect the TH-treated group to achieve targeted temperature within 4h of randomization and to maintain TH for 48h without significant increase in serious adverse effects compared with the control arm.
2. **Analyze the potential lung protective effect of mild TH (core temperature 34°-35°C for 48h) and NMB in patients with ARDS and P/F < 200 compared with controls receiving standard temperature management.** We expect the TH-treated group to trend toward having more 28-day VFDs (primary) and 28-day ICU-FDs, and improved day-3 driving pressure and OSI than the controls.
3. **Evaluate the effects of TH on systemic inflammation and extrapulmonary organ dysfunction.** We expect the treated group to have reduced levels of proinflammatory mediators and lower Sequential Organ Failure (SOFA) scores than controls.

The proposed pilot study will determine whether we can safely include patients with COVID-19 and ARDS in our larger Phase IIb trial of TH and NMB in patients with ARDS. It will help us determine whether the 48h duration of cooling is sufficient.

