- On line 23, indicate whether a proning protocol was started or stopped in the preceding 24 hours.
- Beginning on line 24, record the lowest and highest values for each indicated laboratory value since randomization. If there is only one value, record it in the lowest value field, and click the “Single” box. If there are no data, check the “None” box.
- In the appropriate fields in table beginning on line 25, enter the lowest and highest blood glucose values (from finger sticks) and the date and time of the measurements for each 6-

hour period since randomization. If there is only a single value, record in the “Lowest Glucose” field and check the “Single Value” box for that 6-hour time period. If there are no glucose measurements, click the “None” box for that 6-hour time period.

- If the patient was extubated prior to Study Day 2 (or 3) skip to question 34.
- If intubated and receiving mechanical ventilation for any part of day 2 (or 3) indicate all ventilator modes used in the last 24 hours by checking the appropriate boxes under line 26 and circle the mode used at 0800.
- Indicate whether the patient was extubated in the last 24 hours by checking the appropriate “Yes/No” box on line 27 and, if extubated, enter the time and date in the appropriate fields.
- Record the highest and lowest measured tidal volumes in ml in the last 24 hours in the appropriate fields on line 28.
- Based on the EMR, estimate the total time in hours in the last 24 hours in which tidal volume exceeded 7 ml/kg and record in field on line 29.
- Enter the highest and lowest PEEP and Mean airway pressure in cm H2O in the last 24 hours in the appropriate fields on lines 30 and 31, respectively.
- If still intubated between 0600 and 1000 on study day 2 (or 3), record the plateau pressure and associated PEEP measured in this time interval in the indicated fields beginning on line 32. If multiple values are present, enter the value closest to 0800. If no values from that time period check the “No Values” box. If the patient was not intubated during this time period check the “Not intubated” box.

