- Indicate whether proning protocol was initiated or stopped in the previous 24 hours on line 23.
- Beginning on line 24, record the lowest and highest values for each indicated laboratory value since randomization. If there is only one value, record it in the lowest value field, and click the “Single” box. If there are no data, check the “None” box.
- In the appropriate fields in table beginning on line 25, enter the lowest and highest blood glucose values (from finger sticks) and the date and time of the measurements for each 6-hour period since randomization. If there is only a single value, record in the “Lowest Glucose” field and check the “Single Value” box for that 6-hour time period. If there are no glucose measurements, click the “None” box for that 6-hour time period.
- If the patient was extubated prior to Study 4 skip to question 34.
- If intubated and receiving mechanical ventilation for any part of day 4 indicate all ventilator modes used in the last 24 hours by checking the appropriate boxes under line 26 and circle the mode used at 0800.
- Indicate whether the patient was extubated in the last 24 hours by checking the appropriate “Yes/No” box on line 27 and, if extubated, enter the time and date in the appropriate fields.
- Record the highest and lowest measured tidal volumes in ml in the last 24 hours in the appropriate fields on line 28.
- Based on the EMR, estimate the total time in hours in the last 24 hours in which tidal volume exceeded 7 ml/kg and record in field on line 29.
- Enter the highest and lowest PEEP and Mean airway pressure in cm H2O in the last 24 hours in the appropriate fields on lines 30 and 31, respectively.
- If still intubated between 0600 and 1000 on study day 4, record the plateau pressure and associated PEEP measured in this time interval in the indicated fields beginning on line 32. If multiple values are present, enter the value closest to 0800. If no values from that time period check the “No Values” box. If the patient was not intubated during this time period check the “Not intubated” box.
- If arterial blood gasses are performed, enter the highest and lowest PaO2 and associated FiO2 since randomization in the appropriate fields on line 33. If only a single value enter the

PaO2 and FiO2 values in the “Lowest” field and check the “Single value” box. If no arterial blood gasses were performed, check the “None” box.

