- If the patient was extubated prior to Study 7 skip to question 29.
- Indicate all ventilator modes used in the last 24 hours by checking the appropriate boxes under line 21 and circle the mode used at 0800.
- Indicate whether the patient was extubated in the last 24 hours by checking the appropriate “Yes/No” box on line 22 and, if extubated, enter the time and date in the appropriate fields.
- Record the highest and lowest measured tidal volumes in ml in the last 24 hours in the appropriate fields on line 23.
- Based on the EMR, estimate the total time in hours in the last 24 hours in which tidal volume exceeded 7 ml/kg and record in field on line 24.

- Enter the highest and lowest PEEP and Mean airway pressure in cm H2O in the last 24 hours in the appropriate fields on lines 25 and 26, respectively.
- If still intubated between 0600 and 1000 on study day 7, record the plateau pressure and associated PEEP measured in this time interval in the indicated fields beginning on line 27. If multiple values are present, enter the value closest to 0800. If no values from that time period check the “No Values” box. If the patient was not intubated during this time period check the “Not intubated” box.
- If arterial blood gasses are performed, enter the highest and lowest PaO2 and associated FiO2 since randomization in the appropriate fields on line 28. If only a single value enter the PaO2 and FiO2 values in the “Lowest” field and check the “Single value” box. If no arterial blood gasses were performed, check the “None” box.
- Record total intake in ml in the field on line 29.
- Record the total output (including net volume removed by RRT) in the last 24 hours in the field on line 30.
- Indicate whether the research blood sample was collected by checking the appropriate “Yes/No” box on line 31.
- Record the date and time the research blood sample was collected and processed in the appropriate fields on line 32.
- Indicate how many 0.5 ml aliquots from the sample by checking the appropriate box on line 33.
- Record the time and date the samples were placed in the -80°C freezer in the appropriate field on line 34.
- Indicate the location of the sample in the freezer and the displayed freezer temperature at the time the samples were placed in the indicated fields on line 35.

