- Collect blood and complete CRFs for Day 2, 3, 4, and 7 at 0800 on randomization day + 2, +3, +4, and +7 covering the prior 24h period

SITE ID		PATIENT ID				LETTER CODE			

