**Fluid Management:**

Total Intake since randomization:  mL

Total Output since randomization (include dialysis/CRRT):  mL

Plasma sample collected:  Yes     No

Blood collected: / /   TIME (0-2400)    Processed: / /   TIME (0-2400)

Number 0.5 ml aliquots:  1     2     3     4     5     6     7     8     9     10

Date/Time placed in -80°C freezer: / /   TIME (0-2400)

Location in freezer: \_\_\_\_\_    Temperature reading on freezer: \_\_\_\_\_ °C

SITE ID		PATIENT ID			LETTER CODE		

## DAILY DATA – Day 07

(to be obtained as close to 0800 as possible day 7 after randomization)

Form Completed by \_\_\_\_\_

MONTH			D	D	Y	Y	TIME (0-		

Vital status  Alive  Dead

If Dead Date/Time of death:

MONTH			D	D	Y	Y	Y	Y	TIME (0-2400)

Cause of death (from discharge summary/discussion with ICU team), then skip to question 11.

- Respiratory failure  
  Cardiac (arrhythmia, ACS, cardiogenic shock)  
  Multi-organ failure  
 Refractory shock  
  Intraabdominal (perforation, compartment)  
  Withdrawal of care  
 Neurological devastation  
  Severe sepsis  
  Refractory acidosis  
  Hemorrhage

Still receiving NMB?  Yes  No

If No and discontinued in last 24 hrs, answer following questions:

Date/Time discontinued:

MONTH			D	D	Y	Y	Y	Y	TIME (0-2400)

Reason for discontinuation:  Refractory bradycardia  Possible drug reaction

- Decision of ICU provider  
  Decision of family

Date/Time: neuromuscular function (4 twitches/TOF) returned:

MONTH			D	D	Y	Y	Y	Y	TIME (0-2400)

or  Did not return

Did the patient receive therapeutic hypothermia in last 72 hrs?  Yes  No

If "Yes" how for many hours  and to what temperature (lowest)?  °C

Still intubated or receiving Assisted Breathing?  Yes  No  N/A

If No, when was patient extubated?

MONTH			D	D	Y	Y	Y	Y	TIME (0-2400)

Was RRT started in last 24 hrs?  Yes  No  N/A

If RRT had been previously initiated has it stopped since randomization?  Yes  No  N/A

In the last 24 hrs did the patient have any of the following:

- Bradycardia (with mean arterial pressure < 65 mm Hg or needing pressors)  Yes  No  
 Significant Bleeding (Required IR, Surgery or >3u pRBCs)  Yes  No  
 Diagnosis of new pneumonia  Yes  No

Vital signs in last 24 hrs

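### The Day 03, 04 and 07 forms label plateau pressure as a day-2 reading, against the protocol's own instructions; if staff follow the Day 03 form, day-3 driving pressure could be read 24 h early

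*Protocol*

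**What the plan says.** The protocol appendix has a separate data form for each collection day. On the Day 03, Day 04 and Day 07 forms, the block for plateau pressure and its PEEP carries the same label: "Lung Physiology Parameters (recorded 0600 to 1000 day 2 post-randomization". The same block on the Day 01 form correctly names day 1, so the label is meant to change from form to form.

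The headings under the form titles are also mixed. Day 03 and Day 04 both read "to be obtained as close to 0800 as possible on day 2 after randomization". Day 07 reads "to be obtained as close to 0800 as possible day 7 after randomization", so that form disagrees with its own label.

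Elsewhere the protocol names the matching day:

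- Section 10.5 (Day 2 and 3 forms): "If still intubated between 0600 and 1000 on study day 2 (or 3), record the plateau pressure and associated PEEP".
- Section 10.6 (Day 4 form): "If still intubated between 0600 and 1000 on study day 4, record the plateau pressure".
- Section 10.7 (Day 7 form): "If still intubated between 0600 and 1000 on study day 7, record the plateau pressure".
- The schedule at the end of the Screening/Enrollment/Randomization Source Document tells staff to "complete CRFs for Day 2, 3, 4, and 7 at 0800 on randomization day + 2, +3, +4, and +7".

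Section 7.2 defines driving pressure as plateau pressure minus PEEP. Aim 2 in section 1.2 expects the hypothermia group to show "improved day-3 driving pressure and OSI than the controls". The SAP tests physiological outcomes with a repeated-measures mixed model over days 0, 1, 2, 3, 4 and 7.

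**The concern.** Two current instructions disagree about when a named outcome is measured, and the wrong one is printed beside the field to be filled in. On the Day 03 form the heading and the label agree with each other, so only the form's title points to day 3.

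The plateau-pressure field has no date or time of its own, although fingerstick glucose and the blood sample on the same form do. A value taken from the wrong morning could not be identified from that field.

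If the label were followed, the day-3 value would come from the previous morning. In the hypothermia arm that would usually replace a reading after rewarming with one taken on treatment. Controls receive neuromuscular blockade only as clinically indicated and are not cooled to the study target, so the shift would not affect the two arms alike. With 20 patients randomised 1:1, or about 10 per arm, a few misdated readings would carry weight.

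**Working it through.** **Inputs**

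- Study day 1 runs from randomisation to 0800 the next day and lasts 8 h 1 min to 31 h 59 min (source-document schedule).
- Reference readings are taken between 0600 and 1000, with the value nearest 0800 preferred (section 6).
- Cooling is held for 48 h, with rewarming to 36°C at 0.3°C/h; blockade lasts about 54 h in total (section 8).
- Target temperature is expected within 4 h of randomisation (section 1.2).
- The treatment period is 54 h after randomisation (section 8, usual temperature management arm).

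**Step 1. Reproduce the protocol's figure.** Hours from randomisation to a reading = 24d + c − h, where d is days after randomisation, c the clock hour of the reading and h the clock hour of randomisation (0001 to 2359). For d = 1 and c = 8 this is 32 − h, or 8h01 to 31h59, an exact match.

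**Step 2. Time of each reading.**

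| Reading | 0800 | 0600–1000 window |
|---|---|---|
| Day 2 (as labelled) | 56 − h = 32h01 to 55h59 | 30h01 to 57h59 |
| Day 3 | 80 − h = 56h01 to 79h59 | 54h01 to 81h59 |
| Day 4 | 104 − h = 80h01 to 103h59 | 78h01 to 105h59 |
| Day 7 | 176 − h = 152h01 to 175h59 | 150h01 to 177h59 |

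Taken literally, the label is early by 24 h on the Day 03 form, 48 h on Day 04 and 120 h on Day 07.

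**Step 3. End of treatment in the hypothermia arm.** Rewarming from 35°C takes 1/0.3 = 3.3 h and from 34°C takes 2/0.3 = 6.7 h. Thus 48 h plus rewarming is 51.3 to 54.7 h, consistent with the stated 54 h. Allowing 4 h to reach target, cooling ends at 4 + 48 = 52 h.

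**Step 4. Share of day-2 readings that fall on treatment.** The documents do not give the distribution of randomisation times, so assume it is uniform over 24 h. An 0800 day-2 reading precedes time T when h > 56 − T, a share of (T − 32)/24. For 0600 and 1000, replace 32 by 30 and 34.

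| T | 0800 | Range, 0600–1000 |
|---|---|---|
| 48 h | 16/24 = 66.7% | 58.3 to 75.0% |
| 52 h | 20/24 = 83.3% | 75.0 to 91.7% |
| 54 h | 22/24 = 91.7% | 83.3 to 100% |

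No day-3 reading precedes 54 h, since the earliest is at 54h01. If 4 h to target is added to 48 h and the slowest rewarming (4 + 48 + 6.7 = 58.7 h), 2.9 to 19.6% of day-3 readings would still precede the end of rewarming.

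**The case against.** The strongest reply is that the design is clear and only the forms are wrong. Sections 10.5 to 10.7 are the instructions for completing these forms, and they name study days 3, 4 and 7. The source document schedules the forms on the same days. The repeated day 2 looks like text carried over from another form. Ventilator values come from the standard-of-care record, so a wrong value can be corrected. Driving pressure is a secondary outcome in a 20-patient pilot whose primary outcomes are cooling performance and safety. All of this stands, and it rules out several stronger readings that a reader might infer:

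- **That the day-3 outcome will be a day-2 reading.** The documents support only that it could be, if staff follow the label in place of section 10.
- **That one day-2 value would fill days 2, 3, 4 and 7.** The Day 07 form has a day-7 heading, asks about the preceding 72 h and tabulates days 4 to 7. The Day 04 form asks whether 48 h of cooling were completed, which many patients could not have reached by 0800 on day 2. The 48 h and 120 h displacements are therefore unlikely in practice. The Day 2 form is listed but is not in the supplied text, so its label cannot be checked.
- **That all patients would be measured cold and paralysed.** Controls would not be, as a rule. In the hypothermia arm the day-2 range runs past 52 h and 54 h, so some patients would have finished cooling.
- **That OSI is misdated too.** The label covers plateau pressure and PEEP only; OSI inputs come from separate tables.

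The reply does not remove the contradiction on the Day 03 form. The completion date on line 1 would not reveal a day-2 plateau pressure copied onto a form completed on day 3.

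**Conclusion.** The point holds as an internal inconsistency in the data forms. Five printed references to day 2 (two headings and three labels) conflict with section 10, the form schedule and the Day 07 heading. The practical risk lies mainly with the Day 03 form and the day-3 driving pressure of Aim 2.

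If that form is followed, the reading moves 24 h earlier. For most hypothermia-arm patients it then falls during treatment instead of after it, and it enters the SAP model as day 3. The timing ranges follow from the protocol's own clock; the percentages rest on uniform randomisation times. The documents give no basis for the resulting bias in cm H2O or for how many staff would follow the label, so neither is estimated. The primary outcomes are not affected.

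**What to change.** Change the Day 03 and Day 04 headings, and the lung-physiology labels on the Day 03, 04 and 07 forms, to days 3, 4 and 7 respectively, so that they agree with sections 10.5 to 10.7 and the source-document schedule. Check the Day 2 form at the same time. Add a date and time to the plateau-pressure and PEEP field so that the study day can be verified. For any forms already completed, confirm the plateau-pressure day against the ventilator record before analysis.

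The cost is a minor form revision and one extra field per form. The design and the SAP model do not change.
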